#### 6) Assessment of total exposure to resveratrol:

**Resveratrol:** Resveratrol is widely available as a health food supplement, therefore adherence to the sub-trial requirements to abstain from ingestion of OTC supplements containing resveratrol for the trial duration will be explored in 20% of participants from randomly selected

IRAS: 1005142 Page **33** of **109** 

sites that are willing and able to collect urine samples. Concentrations of urinary resveratrol will be quantified using established HPLC-UV assays.

Accounting for dietary resveratrol consumption in the sub-trial. To ensure that dietary resveratrol is not a confounding factor and examine whether individuals change their behaviour as a result of participating in the trial, we will compare resveratrol intake across trial arms and also at baseline and during the intervention. This will be achieved through the use of Phenol-Explorer, a database containing food composition information on all known polyphenols, which can be used to estimate habitual resveratrol intake from a Food Frequency Questionnaire (88, 89).

#### 2.4 Ethical considerations

The trial will be conducted in full conformance with the principles of the Declaration of Helsinki and to ICH Good Clinical Practice (GCP) guidelines. It will also comply with the Medicines for Human Use (Clinical Trials) Act 2004, subsequent amendments and University of Leicester Standard Operating Procedures (SOPs). All data will be stored securely and held in accordance with ICH GCP, the UK Policy Framework for Health and Social Care, the Data Protection Act and the EU General Data Protection Regulation (GDPR). Written informed consent will be gained prior to entry in the trial. Patient safety and well-being will be paramount and all patients will be treated with respect and dignity throughout the trial.

Participation in a randomised controlled trial means that the participant and clinician are not able to choose all aspects of treatment and a careful explanation of the different treatments and toxicities by arm will be given to participants. The protocol has been designed to reflect the standard care pathway for patients on the BCSP with the minimal number of additional hospital visits and tests (over and above routine care) possible. There will not be any routine reimbursement of costs incurred for patients within the grant however local centres may be able to cover travel and incidental expenses.

A placebo arm has been included in the resveratrol sub-trial to make the treatments seem as similar as possible from the participant's perspective. Importantly, even closer similarity between the trial arms is achieved by preventing investigators knowing which treatment the participant is receiving (double-blind).

For those who experience severe toxicity related to the study drugs and/or those who are unable to adhere to the protocol treatment schedule, active participation in the trial will end at this time. However, they will be asked if they wish to give consent to allow passive follow-up data collection using medical records.

Participants will be followed-up in the long-term through routinely collected healthcare databases provided by National Cancer Registration and Analysis Service (NCRAS) and other organisations. Participants will be asked to consent to this separately and can still participate in the trial if they do not give their consent to this aspect of the trial.

Blood sampling is required to answer trial objectives, and as per routine care some of these tests are required to be fasted. Usual clinical guidance will be followed and sites will be advised to book visits as early in the morning as possible. Section 7.1.1 details additional measures sites will take for patients to arrive fasted for visit 1 consent and baseline screening

IRAS: 1005142 Page **34** of **109** 

assessments. Potential patients will be given the opportunity to come back for a further visit if they are not happy to undergo the consent process in a fasted state. Although rectal biopsies are taken as part of routine care during colonoscopies, this type of sampling poses a theoretical risk of perforation or serious bleeding, though this is rare. Only a very small amount of tissue is required for the research rectal biopsies and will be obtained by trained physicians. Participants will be asked to consent to this separately and can still participate in the trial if they do not give their consent to this aspect of the trial.

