Procedure (Time (T) in weeks)	Pre-trial BCSP colonoscopy	Research visit	Telephone call	Telephone call	Research visit	Surveillance (research)	Post-surveillance colonoscopy
(Time (T) in weeke)	(1)					colonoscopy	telephone call
	-						
		Visit 1	Visit 2	Visit 3	Visit 4	Visit 5	Visit 6
		T= 0 weeks	T= 4 weeks	T= 12 weeks	T= 25 weeks	T= 52 weeks	T= 54 weeks
Colonoscopya	•					•	
Provide trial information (PIS)	•						
Colonoscopy results	● f						•
Eligibility assessment		•					
Informed consent		•					
Medical History and Demographics		•					
Fasting blood samples & processing						_	
-safety & research c		•			•	•	
Blood serum pregnancy test if applicable		•				•	
Food Frequency Questionnaire (FFQ)		•				•	
Concomitant medication recording		•	•	•	•	•	•
Eligibility confirmation & Randomisation		•					
Trial drug dispensing		•b			•		
Provision of urine sample d		•			•	•	
Research faecal sample		•				• (prior to colonoscopy)	
Adverse Events		● e	•	•	•	•	•
Compliance (pill counting)					•	•	
Rectal biopsies						•	
Diagnostic FFPE blocks		•				•	
Last dose of trial drug						•	
End of trial participation							•

<sup>a First colonoscopy is a routine clinical procedure, second colonoscopy is a research procedure. b Patient to commence their trial medication following collection of a baseline research faecal sample (obtained on a FIT kit). cLocally processed: FBC, LFT, U&E, eGFR, HbA1c, fasting lipid profile, glucose. Research samples: insulin, IGFBP-3, IGF-I, PK/PD, exploratory research biomarkers. d Urine will be collected from 20% of patients from randomly selected sites that are willing and able to collect urine. e Adverse events collected from first dose. f Where routine consultations are undertaken remotely following a screening colonoscopy, potential participants will need to be brought into hospital for visit 1.

Visits 2 & 3 have a ±1 week window. Visits 4 and 5 have a ±2 week window. Visit 6 has a +1 week window.

COLO-PREVENT Protocol 11/12/2024: Version 4.0

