#### 7.10 Withdrawal criteria

Every effort should be made by the research team to keep the participants in the trial. However, participants have the right to withdraw their consent to take part in the trial at any time without having to give a reason and this will not affect their future care. Withdrawal of consent details and reasons (if known) should be recorded on the CRF and in the medical notes.

In the unlikely event that a trial participant becomes pregnant during the study, trial treatment will be discontinued. Please refer to section 10.5 for guidance on pregnancy reporting.

The investigator may discontinue treatment of a participant at any time if they are not compliant with the trial protocol or to protect the participant's safety and well-being after consultation with the CI. The IMP may also be discontinued in the case of an adverse event which the investigator considers sufficient to jeopardise the safety of the participant. Participants who discontinue treatment, for whatever reason, will be encouraged to remain in the trial for collection of important outcome and safety data. These treatment ceased participants will be asked to continue attending visits for collection of data and samples. Participants not wishing to attend all subsequent visits, will be asked for their permission to collect data and samples at their exit surveillance colonoscopy. Additionally, some trial assessments (e.g. Food Frequency Questionnaire) may be collected over the telephone if the participant agrees to be contacted. As a minimum, important outcome and safety data will be collected remotely from the participant's medical record. Those declining this will be withdrawn from the trial (thus withdrawing their consent).

Withdrawals from the trial should be discussed with the CI or their deputy and the Trial Manager. If a participant has withdrawn/discontinued from the trial for any reason, then his/her screening and trial ID number(s) cannot be issued to another participant.

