#### **Metformin**

#### Run-in

Undesirable effects of metformin are most frequent during initiation of therapy and usually resolve spontaneously. To prevent them, it is recommended that metformin is taken during or after meals. Metformin does not cause hypo-glycaemia in non-diabetic patients and participants will be reassured about this prior to dosing. Participants will have a run-in period of 4 weeks at the once daily 500 mg metformin dose to allow time for gastrointestinal tolerance. If more than 80% of the prescribed dose is taken during this time, the research team will instruct the participant to increase their dose to twice daily 500 mg metformin tablets.

If the patient does not tolerate the 500 mg metformin then it is possible for the patient to have another 4 week run-in period using a MR formulation 500 mg dose. If this is deemed tolerable then patients will increase their dose to twice daily 500 mg MR release metformin tablets. If the participant is unable to tolerate the lowest dose of metformin then they can continue on the trial with aspirin alone.

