## 11.3 Statistical analysis plan

**Statistical Analysis:** All statistical analyses will be carried out according to a detailed Statistical Analysis Plan (SAP), to be agreed by trial statisticians, the CI, and the TSC. The analysis will primarily follow an intention-to-treat (ITT) approach to the analysis i.e. participants will be analysed in the groups to which they were randomised and not treatment received. Additional analyses to evaluate the extent to which following the protocol is important will be pre-specified in the SAP e.g. per protocol and complier-average causal effects analyses.

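### Sections 2.4 and 7.10 give conflicting follow-up rules after severe toxicity or inability to adhere; where a sub-trial site follows 2.4, the primary outcome is lost

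*Protocol*

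**What the plan says.** Section 2.4 (Ethical considerations) applies one rule to two groups. The first is participants in whom trial medication causes severe toxicity. The second group, and the rule for both, are in these words: "those who are unable to adhere to the protocol treatment schedule, active participation in the trial will end at this time". After that point, "they will be asked if they wish to give consent to allow passive follow-up data collection using medical records". Research visits and the exit colonoscopy are not mentioned for these people.

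Section 7.10 (Withdrawal criteria) sets a different course. "Participants who discontinue treatment, for whatever reason, will be encouraged to remain in the trial for collection of important outcome and safety data". It then gives graded options:

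1. "These treatment ceased participants will be asked to continue attending visits for collection of data and samples".
2. Those who do not want every visit "will be asked for their permission to collect data and samples at their exit surveillance colonoscopy".
3. The minimum is remote collection from the medical record. Only participants who refuse that as well are withdrawn.

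On the colonoscopies, the footnote to Table 2 says of the sub-trial: "First colonoscopy is a routine clinical procedure, second colonoscopy is a research procedure". For the main trial, the Visit 9 text in Section 7.7 lists the exit colonoscopy as a routine clinical procedure. Section 1.1 says first surveillance for high-risk patients has moved from 12 months to 3 years. On analysis, Section 11.3 is primarily intention to treat: "participants will be analysed in the groups to which they were randomised and not treatment received".

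**The concern.** Sections 2.4 and 7.10 apply to the same participants, neither refers to the other, and they lead to different data. Section 2.4 treats severe toxicity or inability to adhere as the end of active participation. Section 7.10 treats it as the end of treatment only.

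In the sub-trial, a participant handled under 2.4 has no week-52 colonoscopy and therefore no polyp count. The reason for the missing count would be how the participant tolerated or took the allocated capsules. Section 1.4.4 describes the commonest reported resveratrol side effects as dose-related and gastrointestinal, and Section 9.7 does not permit dose reduction, so loss could plausibly differ between 1 g, 5 mg and placebo. Those contrasts feed the stop/go decision for each dose in Section 11.6. Outcome loss of that kind weakens a comparison by randomised group even though every observed participant is analysed in the assigned arm. Visit-based safety data after discontinuation would also be lost for the people with severe toxicity, although safety and tolerability of each dose is a secondary objective.

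**Working it through.** **Which rule the rest of the protocol assumes**

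- Section 8.7, metformin run-in: "If the participant is unable to tolerate the lowest dose of metformin then they can continue on the trial with aspirin alone".
- Section 8.9, non-permitted medication becoming indicated: trial drug stops, but the participant is encouraged to stay for outcome and safety data.
- Section 9.9, the equivalent case in the sub-trial: treatment is withdrawn and permission to go on collecting data is requested.
- Sections 8.11 and 9.11: when more than 20% of doses are missed, restarting treatment is left to the investigator. Participation is not ended.
- Section 11.1: people who stop metformin completely because of side effects are counted under crossover, separately from the 15% dropout. The sample size therefore expects outcomes from them.
- Section 11.5: a complier average causal effect analysis is considered if adherence is poor. That needs outcomes from non-adherers.

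Section 2.4 is the exception.

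**Whether records could replace the colonoscopy**

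- Sub-trial: the outcome is due at week 52 from a research procedure, and routine surveillance is at 3 years. Passive records hold no planned 12-month count. The same limit applies to the last option in 7.10, remote record collection, unless the research colonoscopy is done.
- Main trial: the week-154 colonoscopy is routine, so with consent the records can supply the polyp count even under 2.4. Bloods, questionnaires, pill counts and other visit-based data would still be lost.

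**Reproducing the sub-trial sample size (Section 11.1)**

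Inputs: control MPP 1.2, active MPP 0.84, one-sided 10% significance, 80% power, over-dispersion 2.0, 10% dropout, 159 per arm (477 in total).

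Reading over-dispersion as variance = 2 × mean:

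n per arm = (z_α + z_β)² × 2(1/m₀ + 1/m₁) / [ln(m₁/m₀)]²

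- (1.2816 + 0.8416)² = 4.508
- 2(1/1.2 + 1/0.84) = 4.048
- [ln 0.70]² = 0.1272
- n = 4.508 × 4.048 / 0.1272 = 143.4 evaluable per arm
- 143.4 / 0.90 = 159.4, against the stated 159

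The same reading gives 323.7 per arm for the main trial, against the stated 323. Two other readings do not match for the sub-trial: negative binomial k = 2 gives 119 per arm and 1/k = 2 gives 237.

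**Power at assumed levels of total outcome loss, 159 randomised per arm**

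Power = Φ(0.3567 / √(4.048/n) − 1.2816), with n = 159 × (1 − loss).

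| Total loss | Evaluable per arm | Power |
|---|---|---|
| 10% (planned) | 143.1 | 79.9% |
| 15% | 135.2 | 78.2% |
| 20% | 127.2 | 76.4% |
| 30% | 111.3 | 72.2% |

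Only the 10% row comes from the protocol. The other rows are assumptions, with loss taken as equal across arms. The table shows lost precision only and does not measure bias from loss related to treatment.

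**The case against.** The strongest reply is that 2.4 is one sentence in a rationale section, while 7.10 is the section that governs withdrawal and several operative sections agree with it. A site would probably follow 7.10, and nothing shows that any site has done otherwise. This stands as a limit: the loss is conditional on a site following 2.4. It does not remove the conflict, because nothing in the text ranks one section above the other.

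Five stronger readings are tempting, and the protocol does not support them:

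- A reader might infer that 2.4 contradicts the intention-to-treat definition. It does not in wording, since Section 11.3 concerns the group in which people are analysed. The harm is in effect, through missing outcomes.
- A reader might extend 2.4 to any poor adherence. Its trigger is inability to adhere, which is narrower.
- A reader might infer that the main trial also loses its primary outcome. The exit colonoscopy there is routine, and Section 8.7 expressly keeps metformin-intolerant participants in.
- A reader might assume that the imputation rests on data missing at random and so must fail. Section 11.7 states no assumption, and the detail may properly sit in the statistical analysis plan.
- A reader might take adverse-event withdrawals of 6/40 on resveratrol and 4/40 on placebo from one trial in Table 6 and add 15% and 10% to the planned dropout. That gives 159 × 0.90 × 0.85 ≈ 122 and 159 × 0.90 × 0.90 ≈ 129 evaluable, and power of 75.8%. But that trial gave obese adults 100 mg three times daily, which is neither sub-trial dose. The difference is two people, and the same row reports no difference in adverse events between groups. Withdrawal for any adverse event is also not the 2.4 trigger, and the 10% allowance may already include such withdrawals.

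Differential tolerance in the sub-trial is therefore plausible but not shown. Table 6 also lists a 52-week trial at up to 1 g twice daily with no significant difference in adverse events.

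**Conclusion.** The inconsistency is real in the current text and should be corrected. Where a sub-trial site follows 2.4, the primary outcome is lost for reasons connected with tolerance and adherence, and routine records cannot replace it. The main trial is affected mainly in its visit-based data.

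The size cannot be fixed from the protocol, which gives no rate of severe toxicity or inability to adhere in the sub-trial. The design has no reserve at its planned 10% loss, and each further five percentage points of total loss costs roughly two points of power over the range shown. These figures assume variance equal to twice the mean and the planned MPP values of 1.2 and 0.84. Possible bias comes on top and is not quantified. If every site follows 7.10, the rule in 2.4 causes no loss.

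**What to change.** Reconcile the two sections by amending the 2.4 sentence so that stopping trial treatment is separated from stopping outcome follow-up. It should refer to 7.10 and its existing graded options: continued visits, then data at the exit colonoscopy, then remote record collection, with withdrawal only for those who decline all of these. Check that the participant information sheet says the same, and remind sites. No change to when treatment stops is proposed.

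The cost is a short protocol amendment, a document check and a site notice. No procedure is added, since the exit colonoscopy is already scheduled for every participant, and the sample size stays at 477. The change is needed while participants are still in follow-up, because a week-52 colonoscopy that was not done cannot be recovered at analysis.

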#### 2.5 Assessment and management of risk

This trial is categorised as:

• Type B = somewhat higher than the risk of standard medical care

Use of low dose aspirin (75mg) will minimise the risk of adverse events; this is the lowest clinically used dose of aspirin in adults and is well tolerated.

To minimise the chances of GI toxicity, patients randomised to metformin will start at a dose of 500mg once daily and this will be increased after four weeks to the full dose of 500mg twice daily. Patients will be advised to take their tablets with or after food to help with treatment tolerance. If GI toxicities do occur this will be managed by dose reduction of metformin or a switch to a modified release (MR) preparation according to local policy. Following a drug safety update from the MHRA regarding monitoring patients at risk of reduced vitamin B12 levels, annual testing will be required by sites for participants randomised to the aspirin plus metformin arm only.

If participants experience GI symptoms in the resveratrol sub-trial trial, they will be advised to take their full dose with or after food; if symptoms do not improve, they can divide their dose such that two capsules are taken each morning and two in the evening. It will not be possible to manage these patients by reducing the dose without unblinding the trial because participants in the low 5mg resveratrol dose group take one 5mg capsule and three placebo capsules each day.

#### 3. OBJECTIVES AND OUTCOME MEASURES/ENDPOINTS

#### 3.1 Primary objectives

- 1. To assess the benefits and harms of combining metformin and aspirin compared to aspirin alone for the prevention of colorectal polyps in patients with high risk finding identified through the BCSP.
- 2. To assess whether Resveratrol prevents colorectal polyps in high risk individuals and identify the most active dose in a Signal-Seeking sub-trial.

IRAS: 1005142 Page **35** of **109** 

#### 3.2 Secondary objectives

- 1) To assess the safety and tolerability of aspirin and metformin in combination compared to aspirin alone in the main trial.
- 2) To assess the safety and tolerability of each dose of resveratrol compared to placebo in the sub-trial.

#### 3.3 Outcome measures/endpoints

Please refer to sections 1 and 2 for further details and rationale for selection of outcome measures/endpoints.

#### 3.4 Primary endpoint/outcome

Polyp number measured by MPP (Mean number of Polyps per Participant)

#### 3.5 Secondary endpoints/outcomes

#### **Secondary outcome measures**

- Polyp Detection Rate (PDR, proportion of individuals with one or more qualifying\* premalignant polyp(s)at surveillance)
- Advanced polyps (measured as MPP and PDR); these are defined as serrated polyp
  ≥10mm, serrated polyp with any dysplasia, adenoma ≥10mm, adenoma with high-grade
  dysplasia
- Polyp subtype based on histopathology (adenoma/serrated); also reported as MPP and PDR
- Location of polyps (right colon any part of the colon proximal to the splenic flexure; left colon the rectum and the colon distal to and including the splenic flexure)
- Polyp size (maximum dimension in mm as described in the histopathology report or endoscopic size if no histopathological size available)

#### Safety

Adverse events, including clinically significant bleeding episodes and GI tolerability

#### Compliance

 Assessment of compliance by counting residual numbers of tablets/capsules returned by each patient

IRAS: 1005142 Page **36** of **109** 

\* Please refer to definition in figure 2

# 3.6 Exploratory endpoints/outcomes

- Measurement of molecular (glucose, insulin (HOMA), HbA1c, triglycerides, cholesterol, IGFBP-3, free IGF-1) and physical (BMI, waist circumference) markers of metabolic status.
- Assessment of dietary patterns and fat intake using the EPIC FFQ.
- Plasma drug concentrations and metabolite profile for resveratrol and metformin.
- Urinary resveratrol/metabolite levels in 20% participants in the sub-trial from randomly selected sites that are willing and able to collect urine samples.
- In the main trial: Measurement of pharmacodynamic biomarkers common to both aspirin and metformin, including p65, pS6/S6 and cleaved PARP in tissue samples.
- In the resveratrol sub-trial: Analysis of tissue and plasma pharmacodynamic biomarkers, including NQO1, protein carbonyls, Ki67 proliferation index, MLX and CIDEB.
- Characterisation of the gut microbiome.

